## Abstract

---

Rationale: Adolescents living with HIV (ALHIV) have the worst outcomes of all ages because of sub-optimal adherence driven by structural factors associated with poverty. This is exacerbated for adolescents by the limited opportunities to address mental health problems arising from the intersection of growing up in poverty and with HIV. The scientific breakthrough related to Undetectable (viral load) = Untransmissible (virus) has had a major impact on motivation to take up and adhere to antiretroviral therapy among people living with HIV all over the world. However, the discussion remains remarkably silent in high burden, low-income countries (LIC). Very few ALHIV in LIC are aware that having an undetectable viral load (VL) substantially reduces the risk of transmitting HIV to their sexual partners and children.

**Aims:** The aim of the study is to work with MoHCC and other stakeholders to explore whether routine VL testing using DBS can provide sufficiently robust evidence of 'undetectability' to support introduction of U=U messaging in ALHIV.

**The specific objectives are:**

1. To determine viral load fluctuation between routine annual VL testing and the extent to which annual VL using DBS reflects short term fluctuations that occur in the interim.
2. To determine what proportion of ALHIV with VL <1000 copies/uL on DBS have a plasma VL less than 200 copies/uL
3. To explore the reasons for and adolescent's understandings of fluctuations in VL and what a VL<1000 copies/mL means to ALHIV

**Methods:** This mixed method study will be conducted in conjunction with key stakeholders. We will enrol 300 ALHIV with a recent VL<1000 copies/uL in three HIV clinics in Harare and follow them for 12 months. Of these, 100 will be randomly selected to undergo repeat VL testing, using both DBS and plasma samples at enrolment, 6 and 12 months. A purposive sample of twenty will be selected for a longitudinal qualitative study. Additionally, up to eight participatory workshops will be conducted with key stakeholders over the course of the study to co-develop a 'safe' way to message U=U for LIC.

**Potential impact:** The study will provide scientific evidence on whether routine VL testing using DBS as available in LIC can provide sufficiently robust evidence of 'undetectability' and on the variability of an individual's virological response over 12 months. It will provide contextually orientated evidence to inform U=U messaging which has the potential to change the motivation of ALHIV to engage with their treatment and care.

# Introduction

---

## Background and significance

Adolescents living with HIV (ALHIV) have the highest HIV-related morbidity and mortality of any age group as a result of suboptimal adherence to ART (1-4) and are falling far behind the global targets of 90-90-90 (5, 6). The majority of ALHIV live in East and Southern Africa where poverty is an overarching factor that increases vulnerability to, and the impact of, HIV. Poverty includes deprivation, constrained choices, and unfulfilled capabilities, and refers to interrelated features of well-being that impact upon the standard of living and the quality of life (7). Combined data from East and Southern African countries show that only 45% of adolescent girls living with HIV have attained the UNAIDS 90-90-90 virological suppression target (73% of those diagnosed and on treatment should be virologically suppressed) (8). As a result, they are more vulnerable to antiretroviral resistance, treatment failure and progression to expensive second- and third-line regimens than other age groups (9, 10) as well as AIDS related illness and death. A major driver of these high rates of morbidity and mortality is suboptimal adherence, which is in turn driven by a complex web of social and structural factors. It is the poorest and most vulnerable ALHIV who are most at risk of treatment failure (11).

There is now convincing evidence from HIC that people living with HIV who are virologically suppressed are at minimal risk of HIV transmission (12, 13), providing PLHIV with added motivation to optimize their adherence to antiretroviral therapy and enabling them to have intimate sexual relationships without fear of transmitting HIV (13). Despite the transformative effects of U=U, very few ALHIV are aware of the clinical relationship between having an undetectable viral load and rendering the virus untransmissible (13, 14).

To date major operational, funding, logistical and developmental concerns have influenced the absence of the U=U discussion at a policy level within LIC. There is increasing opportunity for these concerns to be overcome, which means that the reticence to explain the implications of viral suppression to adolescents needs to be revisited and adjusted. To capitalize on the value of achieving an undetectable viral load we need to do much more to explain the benefits of this to adolescents to incentivise optimal adherence, but also potentially to support their wellbeing and mental health by highlighting the opportunities that accompany viral suppression. We need to do so by discussing virological suppression/failure within the context of their personal goals and priorities, which are focused on their social and sexual relationships and their capacity for future productivity and reproductivity, goals which may seem more achievable in the context of U=U.

Zimbabwe and many other sub-Saharan countries are transitioning to Tenofovir Disoproxil Fumarate, Lamivudine and Dolutegravir (TLD) from TLE as a first-line regimen in line with the World Health Organization (WHO) recommendation. The transition was due to be completed by December 2020 but may be delayed (or possibly accelerated) in light of COVID19. Recent systematic reviews and meta-analysis conducted have shown that TLD is more potent, suppressing viral load more quickly compared to EFV-based regimens (15, 16). Eighty-one percent of individuals who started with a DTG-based regimen presented a viral load below 50 copies/ml after 3 months of treatment, compared to 61% for those on an EFV-based regimen (15). Furthermore, TLD is more durable, featuring a higher drug-resistance barrier compared to NNRTIs and older integrase inhibitors and thereby reducing the risk of drug resistance (17). Although studies from high income countries have shown an improvement in viral suppression, this is not universal and evaluations to determine TLD's place as first-line and second-line therapy in adolescent and paediatric HIV treatment in low-income setting are ongoing. Of relevance is that adolescent adherence is often related to wider structural concerns rather than simply forgetting to take tablets and so adherence may be poor for prolonged periods of time which TLD may be less able to mitigate. Understanding whether U=U in the context TLD will be critical going forward.

Zimbabwe adopted the WHO guidelines on routine VL testing as standard practice in 2015 amidst several resource and logistical challenges (18-20). These include unsuitable laboratory infrastructure, complex sample collection procedures, transportation of samples to central laboratories from all over the country, unreliable power supply, water supply and air-conditioning; non-adherence to cold chain transportation of the reagents, lack of experienced laboratory personnel and the absence of maintenance contracts for the equipment (19). Although routine coverage of VL testing and monitoring is still erratic the Zimbabwean government has made a commitment to increasing laboratory capacity and aggressively scaling-up VL testing to ensure access to VL testing services by at least 90% of people living with HIV (PLHIV) receiving ART by December 2020. Through support for universal VL testing

from GFATM and PEPFAR, strides have been made in strengthening the laboratory infrastructure, sample transportation, data management, procurement and supply chain management, training and mentorship, quality assurance and monitoring and evaluation which are crucial areas to the success of VL testing scale up (19).

### Research question

The main research question for this study is:

Can messaging relating to Undetectable (viral load) = Untransmissible (virus) change the motivations and adherence of adolescents living the HIV in Africa?

The study therefore aims to answer three key questions: i) what is the evidentiary robustness of a VL 1000c/uL measured using a DBS sample to be considered 'undetectable? ii) what are the perceived risks and opportunities of incorporating U=U into routine HIV treatment and care for adolescents in LIC and iii) can locally acceptable and appropriate ways to integrate the discussion about undetectability into standard of care for ALHIV be developed for Zimbabwe in partnership with stakeholders?

### Rationale

Adolescents living with HIV (ALHIV) have the worst outcomes of all ages because of suboptimal adherence driven by structural factors associated with poverty (2, 8). This is exacerbated for adolescents by the limited opportunities to address mental health problems arising from the intersection of growing up in poverty and with HIV (21). The scientific breakthrough related to Undetectable (viral load) = Untransmissible (virus) has had a major impact on motivation to take up and adhere to antiretroviral therapy among people living with HIV all over the world (13) although even in high income settings the messaging is variable (22). However, the discussion remains remarkably silent in high burden, low-income countries (LIC). Very few ALHIV in LIC are aware that having an undetectable viral load (VL) substantially reduces the risk of transmitting HIV to their sexual partners and children. The study will provide scientific evidence on whether routine VL testing using DBS as available in LIC can provide sufficiently robust evidence of 'undetectability' and on the variability of an individual's virological response over 12 months and between those considered undetectable (<1000) and those undetectable and untransmissible (<200).

U=U messaging has potential enabling effects on adherence and onward disclosure of HIV status but there is very little evidence in Zimbabwe or sub-Saharan Africa on how best the importance of viral load levels and the message of U=U can be communicated to young people and with what implications. There has been limited discussion on whether or how this can be incorporated into routine care in LIC, even for adults. This is in part explained by two things. Firstly, the scarce availability of viral load testing in LIC, where quality of both sampling and testing may be variable. In HIC the U=U message is supported by regular VL testing using plasma samples with a cut off for 'undetectability' of <200copies/uL (although the PARTNER study which looked at transmission in 551 heterosexual partners also found no transmission between partners where the index case had a VL of 200-1000 c/uL (14)).

Secondly, the lack of U=U discussions may reflect reticence and possibly stigma among the community delivering HIV care and support to ALHIV about whether young people would respond responsibly to this information; they are uneasy about the potential disruptive effects of this message (22). Whether it is advisable to promote U=U also rests on young people's likely understanding of the messaging; currently there is little knowledge of how an undetectable VL might be interpreted by ALHIV in LIC, what it means for them and their futures and whether it motivates or undermines their intention to adhere. With limited opportunity for ongoing or more nuanced discussion about their illness, their understanding of HIV is often static and may not be updated in response to scientific advances or to meet their evolving needs, depriving ALHIV of the opportunity to develop their understanding of the changing nature of the management of HIV or the benefit of the changing meanings of HIV. U=U may ameliorate stigma associated with it (22). This study will provide contextually orientated evidence to inform U=U messaging to guide both policy makers and healthcare workers on how U=U can be integrated in the routine care of ALHIV in Zimbabwe. The study will also be relevant to other comparable LIC in the region.

### Aim

The study aims to provide scientific evidence on whether routine VL testing using DBS as available in LIC can provide sufficiently robust evidence of 'undetectability' and on the variability of an individual's

virological response over 12 months and between those considered undetectable (<1000) and those undetectable and untransmissible (<200). We therefore propose to conduct a longitudinal study to i) determine at what 'threshold' U=U might be safely promoted in this setting; ii) explore ALHIV's understanding and or interpretation of the VL results. The study will also explore responsible ways to disseminate this message to ALHIV living in Zimbabwe, and across the Southern African region.

Our specific objectives are:

1. To determine viral load fluctuation between routine annual VL testing and the extent to which annual VL using DBS reflects short term fluctuations that occur in the interim.
2. To determine what proportion of ALHIV with viral load <1000 copies/uL on DBS have a plasma VL less than 200 copies/uL
3. To explore the reasons for and adolescent's understandings of fluctuations in VL (measured using standard of care DBS) and what a VL<1000 copies/mL means to ALHIV
4. To explore the perceived risks and opportunities of incorporating U=U into routine HIV treatment and care for ALHIV in LIC
5. To explore with key stakeholders the implications of our findings for the feasibility and framing of the U=U message in LIC for ALHIV.

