### Study design and setting

A longitudinal mixed method study will be conducted in Harare City Health Department at three high volume clinics (BRIDH, Kuwadzana and Rujeko). All the clinics provide care as part of the Paediatric Opportunistic Infection and Antiretroviral Therapy program (OI/ART) and started conducting routine viral load testing in 2016. BRIDH has capacity for onsite VL testing. The three clinics are situated in the low-income and overpopulated residential suburbs which are ranked among the poorest residential areas in Harare (Mbare, Kuwadzana and Dzivarasekwa). The clinics mainly serve people from poor households. BRIDH is located in Mbare residential suburb which is one of the oldest and most impoverished residential suburbs in Zimbabwe.

**Aim 1 and 2: To determine viral load fluctuation between routine annual VL testing and the extent to which annual VL using DBS reflects short term fluctuations that occur in the interim and to determine what proportion of ALHIV with viral load <1000 copies/uL on DBS have a plasma VL less than 200 copies/uL**

The study will explore the sensitivity of viral load testing so that decisions can be made on the best use of resources in optimizing the care and support that can be given to ALHIV in the region. This component will utilize primary and secondary data. Three hundred ALHIV with a recent VL<1000 copies/uL will be randomly selected from clinic registers complete a structured questionnaire. Interviews will explore demographic characteristics, self-reported ART adherence and knowledge of U=U. In depth analysis of ALHIV' VL trajectories will be conducted on a randomly selected sub sample of 100 ALHIV using 6 monthly finger prick DBS and plasma VL sampling to provide evidence on the fluctuation in an individual's virological response over 12 months and how this differs between those considered virologically suppressed (<1000 copies/uL) and those undetectable and untransmissible (<200 copies/uL). Secondary data will be collected from clinic records on HIV treatment history, drug regimens, VL testing (include VL at enrolment and 12 months).

**Aim 3: To explore the reasons for and adolescent's understandings of fluctuations in VL (measured using standard of care DBS) and what a VL<1000 copies/uL means to ALHIV.**

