### Responsibilities

Data management will take place at CeSHHAR Zimbabwe led by JD under the direction of principal applicant. The principal applicant and research team will be responsible for ensuring good quality data are collected.

**Data analysis:** Quantitative data will be analysed using STATA 15.0. Descriptive summaries and frequencies of social, clinical and demographic characteristics by different VL trajectories will be conducted. All qualitative interviews will be conducted by the PI in Shona, audio-recorded, transcribed verbatim, and translated into English. Iterative data collection and analysis will be conducted. Preceding interviews will inform subsequent interviews. Data will be uploaded, coded and summarized using a qualitative software package (NVivo 9.0, QSR International). Data analysis will be conducted using thematic and constant comparison analytical approaches (23). In the initial stages I will adopt a thematic approach to explore emerging themes followed by adopting a constant comparison approach within and across and between different participants.

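### Objective 2 cuts plasma viral load only at 200, so it tests DBS <1000 against the 200 standard but says little about a threshold of 1000

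*Combined protocol and SAP*

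**What the plan says.** Viral load cut points are given here as bare numbers, in the protocol's units.

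- **Objective 2.** The Abstract, the Aim section and Study design and setting all state it with the same single plasma cut. The Aim section has "To determine what proportion of ALHIV with viral load <1000 copies/uL on DBS have a plasma VL less than 200 copies/uL".
- **The decision it serves.** The Aim section proposes a longitudinal study to "determine at what 'threshold' U=U might be safely promoted in this setting". The first key question under Research question is "what is the evidentiary robustness of a VL 1000c/uL measured using a DBS sample to be considered 'undetectable".
- **The standard.** The Rationale gives <200 in plasma as the cut-off for undetectability in high-income settings. The Aim section and the Expected outcomes section label <200 as both undetectable and untransmissible. The Rationale then adds, in parentheses, that one partner study "also found no transmission between partners where the index case had a VL of 200-1000 c/uL".
- **Other use of the two cuts.** Study design and setting plans six-monthly DBS and plasma sampling in 100 participants, to describe fluctuation over 12 months and "how this differs between those considered virologically suppressed (<1000 copies/uL) and those undetectable and untransmissible (<200 copies/uL").
- **Analysis.** The data analysis paragraph under Responsibilities says "Descriptive summaries and frequencies of social, clinical and demographic characteristics by different VL trajectories will be conducted". It describes no cross-tabulation of DBS against plasma.

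**The concern.** Among participants with DBS <1000, Objective 2 creates two plasma classes: below 200, and everything else. The second class mixes results of 200-999 with results of 1000 or more. For a study that treats the threshold as an open question, these mean different things. If the remainder lies at 200-999, DBS <1000 has at least been matched by plasma <1000, and the Rationale's remark on 200-1000 becomes relevant. If much of it lies at 1000 or more, DBS <1000 does not reliably indicate plasma <1000, and that remark offers no cover. The Objective 2 percentage is the same in both cases.

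The results are to be discussed with policy makers and health workers in the workshops, and the Dissemination section hopes to see the messaging enter national implementation guidelines. Those audiences would need the split in order to discuss a threshold of 1000. Planning it in advance also avoids choosing the breakdown after seeing the data.

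**Working it through.** **Inputs from the protocol.** Paired plasma and DBS samples come from 100 participants at enrolment, 6 and 12 months (Procedures, Quantitative interviews). The plasma cut in Objective 2 is 200. The DBS condition is <1000. The protocol gives no expected value for Objective 2, so there is no stated figure to reproduce. The cohort size of 300 concerns the questionnaire sample and does not bear on this point.

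**Step 1: what Objective 2 leaves undetermined.** Among those with DBS <1000, let p be the proportion with plasma <200, q with plasma 200-999 and r with plasma >=1000. Then p + q + r = 1, and Objective 2 reports p only. Hence q + r = 1-p, and r can be anything from 0 to 1-p:

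| Objective 2 result p | Possible range for r |
|---|---|
| 80% | 0-20% |
| 90% | 0-10% |
| 95% | 0-5% |

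**Step 2: illustration.** The counts are assumptions: 95 of the 100 have DBS <1000 at a given visit, and 85 of those have plasma <200. Intervals are two-sided 95% Clopper-Pearson. For k out of n, the lower limit is the 2.5% point of Beta(k, n-k+1) and the upper limit is the 97.5% point of Beta(k+1, n-k). For k = 0 the lower limit is 0 and the upper limit is 1 - 0.025^(1/n).

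| Split of the 95 (<200 / 200-999 / >=1000) | Objective 2 | Plasma >=1000 |
|---|---|---|
| 85 / 10 / 0 | 89.5% (81.5-94.8) | 0% (0-3.8) |
| 85 / 5 / 5 | 89.5% (81.5-94.8) | 5.3% (1.7-11.9) |
| 85 / 0 / 10 | 89.5% (81.5-94.8) | 10.5% (5.2-18.5) |

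For the zero count, 1 - 0.025^(1/95) = 0.038. The Objective 2 column never changes. The >=1000 intervals at the two extremes do not overlap, but the middle row overlaps both.

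**Step 3: other assumed counts.** Take all 100 with DBS <1000 and 80 with plasma <200. Objective 2 is 80% (70.8-87.3). Plasma >=1000 is then 0% (0-3.6) for a split of 80/20/0, 10% (4.9-17.6) for 80/10/10, and 20% (12.7-29.2) for 80/0/20.

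**Step 4: does other text supply the split?** The comparison in Study design and setting concerns fluctuation over 12 months. Its groups, <1000 and <200, are nested. It does not say that the cuts apply to plasma, and it defines no class of plasma >=1000. The same section mentions exploring the sensitivity of viral load testing, without a reference cut or a definition. The data analysis paragraph names no table of one sample type against the other.

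**The case against.** The strongest reply is that 200 is the protocol's own standard. Objective 2 asks how often DBS <1000 meets it, and on those terms any plasma result of 200 or more fails, wherever it falls. The protocol never adopts 200-999 as acceptable; the band appears in one parenthetical remark, with no denominator or interval. This stands. Objective 2 is a proper question and its <200 proportion should be kept. What the reply does not cover is the stated aim of finding a threshold and the key question about 1000, which go beyond checking against 200.

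A reader might infer that the paired samples serve no purpose but Objective 2, or that plasma >=1000 could never be estimated. The documents do not support that. Study design and setting plans further, loosely described, analyses of the paired data using both cuts. If plasma is recorded as a number, the split can be made later from the same samples. The supportable statement is that it is not explicitly planned.

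A reader might also infer that the same Objective 2 figure leads to opposite conclusions. That arises only in assumed extremes, with the whole remainder on one side of 1000, and the protocol sets no acceptance criterion by which 0% or 10.5% would count as support or refutation. The ambiguity is also capped at 1-p, so a result near 100% would leave little to resolve.

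Finally, the data analysis paragraph is brief for every objective, so this is partly one instance of a general lack of detail.

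**Conclusion.** The point holds as a gap in the stated objective and analysis, not in data collection. As written, Objective 2 assesses DBS <1000 against the 200 standard and is only weakly informative about a threshold of 1000, because the share with plasma >=1000 is bounded only by 0 and 1-p. In the illustration that range runs from 0/95 (0-3.8%) to 10/95 (5.2-18.5%). Those counts are assumed and the true split is unknown. The importance depends on p: modest at 95% or above, where at most 5% is hidden, and larger as p falls.

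The conclusion rests on two readings: that the threshold is a real question for this study, as the Aim and Research question sections say, and that the fluctuation comparison is not a plan for the missing table. It does not rest on any view of which threshold is right. The change is worth making because it is nearly free and bears directly on the study's first aim.

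**What to change.** Keep the <200 proportion as it is. Restate Objective 2, wherever it appears, to report three plasma bands (<200, 200-999, >=1000) among participants whose DBS result is <1000 at the same visit. Add the matching table to the data analysis paragraph.

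Report the bands separately at enrolment, 6 and 12 months, each with its denominator and a two-sided exact 95% CI. If visits are pooled, a person can contribute up to three pairs and a simple exact binomial interval is not valid. Use an interval that allows for repeated pairs, such as a cluster-robust interval or a bootstrap that resamples participants. State that plasma viral load will be recorded as a number, so that both cuts can be applied.

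The cost is a wording change and one more table, with no extra samples or tests. The intervals will be wide: at 100 participants the half-width is about 9.8 percentage points for a proportion of 50% (1.96 x sqrt(0.25/100)), and even zero cases of plasma >=1000 among 95 would leave up to 3.8% compatible with the data.
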